8.7.3 Exploratory Efficacy Endpoints and Analyses

The below planned analyses on the exploratory efficacy endpoints will be performed only on the ITT subjects who meet the following two criteria:

- A sample of the exploratory efficacy parameter is available at Baseline (V2) visit
- At least one follow-up sample of the exploratory efficacy parameter is available either at Week 12 (V5) visit or at Week 24 (V7) visit

• Absolute and percent change in serum C4 and FGF19 from baseline to Weeks 12 and 24 visits.

Absolute serum C4 values as well as absolute and percent changes from baseline to Week 12 and Week 24 visits in serum C4 values will be provided at baseline, Week 12 and Week 24 visits for each allocated treatment group using summary statistics. FGF19 values will be summarized similarly.

• Absolute and percent change in serum IL-6, CK-18 M30, and CK-18 M65, from baseline to Weeks 12 and 24.

The summaries on serum IL-6 and CK-18 M30 and M65 fractions will be similar to those abovedescribed for serum C4.

• Absolute and percent change in serum IgM, IL-4, IL-12, IL-17A, and interferon γ, from baseline to Weeks 12 and 24.

The summaries on serum IgM, IL-4, IL-12, IL-17A, and interferon γ will be similar to those above-described for serum C4.

• Assessment of additional biomarkers of interest.

If relevant, data-driven analyses on additional biomarkers of interest will be performed. If performed, these post-hoc analyses will be described in a SAP Change Log and the results will be included in the exploratory efficacy analyses.

• Assessment of metabolomics signatures.

If relevant, metabolomics analyses will be performed. If performed, these analyses will be outlined in a separate analysis plan and reported in a dedicated study report included as an appendix to the clinical study report.

• Assessment of pharmacogenetics.

If relevant, pharmacogenetics analyses of interest will be performed. If performed, these analyses will be outlined in a separate analysis plan and reported in a dedicated study report included as an appendix to the clinical study report.

8.7.4 Subgroup Analysis

Subgroup summaries/analyses will be performed using the following subgroups of interest:

- Subgroups of interest 1: subjects with GGT values below and above the stratification cut off value (≥2.5xULN) (for the primary efficacy endpoint analysis only)
- Subgroups of interest 2: subjects with hsCRP value below and above the ULN at Baseline (for the analysis of hsCRP only).

- Subgroups of interest 3: subjects with ELF score value below 9.8 at Baseline and subjects with ELF score value equal to or greater then 9.8 at Baseline (for the analysis of ELF scores only).
- Subgroups of interest 4: subjects with liver stiffness value below 9.6 kPa at Baseline and subjects with liver stiffness value equal to or greater than 9.6 kPa at Baseline (for the analysis of liver stiffness only).
- Subgroups of interest 5: subjects with any Baseline pruritus VAS value and subjects with a Baseline pruritus VAS value greater than 0.

For each subgroup of interest, any subject with a missing/unknown result will be excluded from the subgroup summaries/analyses.

Subgroup summaries/analyses will only be performed for a minimum subgroup size of at least 20% of the analyzed population, unless otherwise specified.

For a given endpoint, the subgroup summaries/analyses will be run on each of the analysis populations considered for the global summaries/analyses unless otherwise specified.

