5.4 SAMPLE SIZE JUSTIFICATION

A sample size of 34 randomly allocated and treated subjects within each treatment group with an overall sample size of 102 subjects will have 80% power to detect a 28% difference in the means of the percent change from baseline in serum GGT. A Wilcoxon Mann-Whitney test has been used for the sample size estimate because this represents the worst-case scenario with regards to the statistical power. A standard deviation of 30 for the active GKT137831 group and a standard deviation of 40 for the placebo group have been assumed based on a recent phase 3 clinical trial of OCA [1].

An overall two-sided Type I error of 5% has been considered for the sample size calculation. The Hochberg method will be used to adjust the alpha level for multiple comparisons. Therefore, the first dose level comparison at the final analysis will be tested against an alpha level of 0.04695 and the second dose level will be tested against an alpha level of 0.023475. The alpha level of 0.023475 has been used for the sample size calculation.

The sample size calculation assumes all subjects (including withdrawals) will be included in the analysis. As a result, there has been no adjustment for dropouts.

6 Statistical Considerations

The SAS system version 9.4 (or higher), will be used for all analysis, unless otherwise specified.

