8.7 EFFICACY DATA ENDPOINTS AND ANALYSES

8.7.1 Primary Efficacy Endpoint and Analyses

The clinical response to GKT137831 is defined as the percent change from baseline to Week 24 visit in serum GGT (primary efficacy endpoint).

Absolute serum GGT values as well as absolute change and percent change from baseline to Week 24 visit in serum GGT values will be provided at baseline and Week 24 visit for each allocated treatment group using summary statistics.

Due to the small sample size, the primary analysis will be conducted using a stepwise approach. The percent change from baseline to Week 24 visit in serum GGT will be analyzed using an Analysis of Covariance (ANCOVA) with the allocated treatment and disease severity at baseline as fixed effects, and the serum GGT baseline value as a continuous covariate.

The least square means estimate of the difference between each dose of GKT137831 and placebo alongside the 95% confidence interval will be calculated. Given two doses of GKT137831 are tested versus placebo, the 97.5% confidence interval of the least square mean of the difference between each dose of GKT137831 and placebo will also be calculated to account for the multiple testing using Hochberg adjustment.

If the normality assumption for the primary analysis is not met then the percent change from baseline in serum GGT at Week 24 will be analyzed non-parametrically through a stratified Wilcoxon Mann-Whitney (van Elteren) test. The normality assumption will be assessed through the examination of diagnostic residual plots.

The primary analysis will be performed using the ITT population and a sensitivity analysis will be done using the PP population. If the Wilcoxon Mann-Whitney test is used, a subgroup analysis for disease severity will also be performed.

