8.7.2 Secondary and Tertiary Efficacy Endpoints and Analyses

Any analyses of the secondary and tertiary efficacy endpoints should be interpreted with care. The study has not been powered for the interpretation of these endpoints. Inferential statistical analyses performed on the secondary endpoints are included to aid interpretation and should not be considered as an alternative to the primary analysis for determining efficacy.

All the analyses on the secondary and tertiary efficacy endpoints will be performed on the ITT population.

The need for sensitivity analyses of the secondary endpoints on the PP population will be assessed after the blinded review of the major protocol deviations.

Secondary efficacy endpoints

The summaries and analyses planned for the secondary efficacy endpoints are described below.

Template Author: [name] Version 3.0 16AUG2017

• Absolute and percent change in serum GGT from baseline to each post-baseline assessment.

Absolute serum GGT values as well as absolute change and percent change from baseline in serum GGT will be provided at baseline and each post-baseline visit for each allocated treatment group using summary statistics.

The percent change from baseline to each post-baseline visit in serum GGT will be analyzed using a repeated measures ANCOVA model with the allocated treatment, the post-baseline visit and disease severity at baseline as fixed effects, the baseline serum GGT as a continuous covariate, and the interaction effect between treatment and visit.

Estimation will be performed using SAS[®] PROC MIXED with LSMEANS and REPEATED statement. An unstructured covariance matrix will be selected for the repeated measure analysis.

The least square means estimate of the percent change from baseline in serum GGT considered at each post baseline visit alongside its two-sided 95% CI and 97.5% CI will be presented as well as the associated standard error and the two-sided p-value.

Should the repeated measures analysis not converge or the normality assumption fail, data from each visit will be compared separately using the same method as the primary analysis.

• Absolute change in ELF score from baseline to Weeks 12 and 24 visits

Absolute ELF scores and absolute changes from baseline to Weeks 12 and 24 visits in ELF scores will be provided at baseline, Week 12 and Week 24 visits for each allocated treatment group using summary statistics.

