Only data collected for these subjects, prior to and including the date of the Week 6 visit for the last randomized subject included in the interim analysis cohort, will be taken into consideration for the interim analysis.

The purpose of the interim analysis is to support decision-making regarding the further development of GKT137831. It is not intended to amend the study protocol or stop the trial due to futility or overwhelming efficacy.

The primary efficacy endpoint of the interim analysis is the percent change from baseline to Week 6 visit in serum GGT.

The interim analysis will only be run on this primary efficacy endpoint and on the following secondary efficacy endpoints (no other endpoint will be analysed):

- Absolute change from baseline to Week 6 visit in serum GGT
- Absolute and percent change from baseline to Week 6 visit in serum levels of ALP
- Absolute and percent change from baseline to Week 6 visit in serum levels of hsCRP and fibrinogen
- Absolute and percent change from baseline to Week 6 visit in serum levels of ALT, AST, conjugated and total bilirubin.
- Absolute and percent change from baseline to Week 6 visit in the FIB-4 and APRI scores.

The interim analyses will also be run for the following 4 subgroups of interest:

- Subgroups of interest 1: subjects with GGT values below and above the stratification cut off value (≥2.5 x ULN) (for the primary efficacy endpoint of the interim analysis only). If only very few subjects have a Baseline GGT below 2.5 x ULN then the stratification cut off value for the analysis will be the median GGT at Baseline.
- Subgroups of interest 2: subjects below and above 65 years of age (for the primary efficacy endpoint of the interim analysis only)
- Subgroups of interest 3: subjects with ALP value below and above median at Baseline (for the primary efficacy endpoint of the interim analysis only)
- Subgroups of interest 4: subjects with hsCRP value below and above the ULN at Baseline (for the analysis of hsCRP only)

Subgroup summaries/analyses will only be performed for a minimum subgroup size of at least 20% of the interim analysis population, unless otherwise specified.

In addition, the gender and the age as well as the serum GGT, the serum levels of ALP, ALT, and hsCRP values will be summarized at Baseline for each allocated treatment group.

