The interim analysis will be conducted by the unblinded SMB statistician, who has no involvement with the study conduct. The interim analysis outputs will be communicated to the Sponsor's Chief Medical Officer.

The interim analysis described above does not include assessments of safety data. The safety data will be reviewed periodically and separately as described in the study SMB charter.

10 Changes to Planned Analyses

The final analysis will be performed according to a 2-stage process detailed in Section 6.1.

11 Document History

Date	Version	Modified by	Brief details of changes made to template
150CT2018	1.0	[name]	Initial final version
15MAR2019	2.0	[name]	Updated final version The main changes are the following: 1. Addition of Section 6.1 to clarify the timing of the final analysis. 2. Addition of Appendix 1 to provide the list of Top Line tables.

12 References

[1] New Drug Application (NDA) 207999 submitted by Intercept Pharmaceuticals, Inc. for obeticholic acid (OCA) proposed for the treatment of Primary Biliary Cirrhosis (PBC), Gastrointestinal Drug Advisory Committee (GIDAC) Meeting, April 7th, 2016.

[2] Hirschfield GM et al. Efficacy of Obeticholic Acid in Patients With Primary Biliary Cirrhosis and Inadequate Response to Ursodeoxycholic Acid. Gastroenterology 2015; 148: 751-761.

[3] CTCAE v4.03:

http://evs.nci.nih.gov/ftp1/CTCAE/CTCAE_4.03_2010-06-14_QuickReference_5x7.pdf

13 Appendix 1: List of Top Line tables

Table order	Table number	Table title
1	14.1-1	Subject Disposition (Randomized Population)
2	14.1-3	Summary of Demographic and Baseline Characteristics (ITT Population)
3	14.1-5.1	Disease Characteristics (ITT Population)
4	14.2-1.1.1	Summary of Absolute and Percent Change from Baseline to Week 24 Visit in Serum GGT (ITT Population)
5	14.2-1.1.2	Analysis of Percent Change from Baseline to Week 24 Visit in Serum GGT (ITT Population)
6	14.2-1.3.1.1	Summary of Percent Change from Baseline to Week 24 Visit in Serum GGT by Subgroup of Baseline GGT values (ITT Population)
7	14.2-1.3.1.2	Analysis of Percent Change from Baseline to Week 24 Visit in Serum GGT by Subgroup of Baseline GGT values (ITT Population)
8	14.2-2.1.1	Summary of Absolute and Percent Change from Baseline to each Post- Baseline Visit in Serum GGT (ITT Population)
9	14.2-2.1.2	Analysis of Percent Changes from Baseline in Serum GGT across all Post Baseline Visits [a] Model Estimates (ITT Population)

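### GGT-stratum analyses of the primary endpoint are unconditional in SAP 8.7.4 and the top-line tables but conditional in SAP 8.7.1 and the protocol, and no treatment-by-subgroup comparison is planned at the final or interim analysis

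*SAP*

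**What the plan says.** The plan gives two rules for the same subgroup analysis.

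- Conditional: SAP 8.7.1, matching protocol 10.4.3.2, says "If the Wilcoxon Mann-Whitney test is used, a subgroup analysis for disease severity will also be performed". Otherwise protocol 10.4.3.3 provides only descriptive statistics by severity and by subgroups named in the SAP.
- Unconditional: SAP 8.7.4 lists "subjects with GGT values below and above the stratification cut off value (≥2.5xULN) (for the primary efficacy endpoint analysis only"). Appendix 1 carries it into the top-line package as Table 14.2-1.3.1.2, "Analysis of Percent Change from Baseline to Week 24 Visit in Serum GGT by Subgroup of Baseline GGT values (ITT Population"), next to a descriptive companion table.

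SAP 10 declares only the two-stage database lock as a change to the planned analyses. SAP 8.7.4 requires a subgroup to hold at least 20% of the analysed population, and it repeats subgroup analyses in each population used for the overall analysis.

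At the interim, SAP 9 splits Week 6 GGT by GGT stratum, by baseline ALP median and by age: "subjects below and above 65 years of age (for the primary efficacy endpoint of the interim analysis only"). The GGT cut-off moves to the median if very few subjects fall below 2.5 x ULN. Protocol 10.3 lists no interim subgroups but leaves the contents to the SAP.

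On error control, SAP 5.4 states "An overall two-sided Type I error of 5% has been considered for the sample size calculation". Under Hochberg, the first dose comparison is tested at 0.04695 and "the second dose level will be tested against an alpha level of 0.023475". These levels are written for the overall dose-placebo contrasts. The caution in SAP 8.7.2, "Any analyses of the secondary and tertiary efficacy endpoints should be interpreted with care", does not mention subgroups of the primary endpoint. No subgroup test level, interaction term or exploratory status is given in SAP 8.7.4 or SAP 9.

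**The concern.** Two things are at stake. First, whether the stratum analysis is run at all differs between sections of the SAP. Under 8.7.1 it depends on a residual-plot judgement; under 8.7.4 and Appendix 1 it always appears, close behind the primary result in the top-line tables.

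Second, the question a stratum analysis should answer is whether the effect differs by baseline GGT. Separate analyses without an interaction estimate do not answer it. They give each dose two results based on few subjects, and the natural reading is to see which one reaches significance. With the planned sample size, one stratum will often be significant and the other not even when the drug works equally in both. If the overall test fails, a nominally significant stratum result on the same endpoint would sit beside it with nothing marking its status. At the interim, similar tables feed decisions about further development.

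**Working it through.** **Inputs from SAP 5.4.** 34 per arm, 1:1:1; SD 30 active and 40 placebo; difference 28 points; two-sided 5%; Hochberg levels 0.04695 and 0.023475 (0.04695 / 2 = 0.023475). The share of subjects below 2.5 x ULN is not given. I assume 20-50%, the lower bound being the 20% rule. The level at which a subgroup p-value would be read is not given either; I assume two-sided 5% unless stated.

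**The plan's own figure.** The plan says 34 per arm will "have 80% power to detect a 28% difference in the means of the percent change from baseline in serum GGT". Root-mean-square SD = sqrt((30² + 40²)/2) = 35.36. With Wilcoxon efficiency 3/π, the effective n is 34 × 3/π = 32.5. Noncentrality = 28 / (35.36 × sqrt(2/32.5)) = 3.19. At alpha 0.023475, power is 80.5% (noncentral t); a simulated Mann-Whitney test gives 79.8%. The stated 80% is reproduced.

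**Final analysis, no effect.** Two strata × two doses = 4 tests. If independent, 1 − 0.95⁴ = 18.5%. Because the doses share a placebo arm, the simulated figures are slightly lower (60,000 to 100,000 trials per setting).

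| Reading | Overall Hochberg test or any stratum test positive |
|---|---|
| Both strata, each test at 5%, equal SDs | 18% |
| Both strata, each test at 5%, SAP SDs | 17% |
| Hochberg applied within each stratum | 10.6-11.0% |
| One stratum under 20% and dropped, tests at 5% | 9.4-9.9% |
| Overall Hochberg test alone | 4.3-4.6% (at most 4.695% by design) |

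The overall test fails while a stratum test is positive in about 12-14% of null trials with both strata, and 4-5% if the low stratum is dropped.

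**Interim, no effect.** 80-90% of 102 is about 27-30 per arm. Three factors × two levels × two doses = 12 subgroup tests. If independent, 1 − 0.95¹² = 46.0%. The factors overlap, so the simulated chance of any positive Week 6 GGT test, including the two overall contrasts, is lower.

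| Reading | Any positive |
|---|---|
| All six subgroups at 5%, equal SDs | 36-37% |
| All six subgroups at 5%, SAP SDs | 34-35% |
| Age 65 and over dropped | 31% |
| One age and one GGT subgroup dropped | 24% |
| Hochberg applied to the overall contrasts and in each subgroup | 21-22% |
| Two overall contrasts alone, each at 5% | about 9% |

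**Final analysis, identical 28-point effect in both strata.** For m subjects per arm in a stratum and SD 35, the standard error is 35 × sqrt(2/m), and power is that of a two-sided 5% t-test with 2m − 2 degrees of freedom. With stratum powers p and q, the chance that a given dose is significant in exactly one stratum is p(1 − q) + q(1 − p).

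| Split per arm | Standard errors | Powers | Exactly one significant |
|---|---|---|---|
| 17 / 17 | 12.0, 12.0 | 0.62, 0.62 | 47% |
| 12 / 22 | 14.3, 10.6 | 0.47, 0.74 | 52% |
| 7 / 27 | 18.7, 9.5 | 0.28, 0.82 | 64% |

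The SAP's SDs give 48-64%. Simulations range from about 45% to 64%, depending on the share and the variance estimate.

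**Precision of the interaction.** Its standard error is the root sum of squares of the two stratum standard errors: sqrt(12.0² + 12.0²) = 17.0 for 17/17 and sqrt(18.7² + 9.5²) = 21.0 for 7/27. The 95% half-widths (× 1.96) are about 33 and 41 points.

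**The case against.** The strongest reply is that nothing confirmatory is at risk. The primary analysis is the overall ITT contrast for each dose under Hochberg, and no section lets a subgroup result establish efficacy. That stands. A reader might infer that the trial's false-positive rate is 18%, or 36% at the interim. The documents do not support this: those figures are the chance of any nominally significant entry in a set of tables, not the error of the primary conclusion, which stays at or below 4.695%.

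The percentages also depend on readings the SAP does not fix. It gives no subgroup test level. The 20% rule may remove the low stratum, which is plausible because entry already requires GGT of at least 1.5 x ULN and SAP 9 itself allows for very few subjects below 2.5 x ULN. The interim is stated not to stop or amend the trial, and its two unadjusted overall contrasts already carry about 9%. All of this stands, and it is why ranges are given.

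No rule says that effect differences will be judged by which stratum is significant, so the 45-64% describes what such a reading would produce, not a planned decision. Finally, the van Elteren test has no treatment-by-stratum term, so an ANCOVA interaction cannot replace the stratum analysis in the one case where the protocol requires it. The fix has to allow for that.

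The objection does not remove the conflict between the two rules or the absence of any estimate of how the effect differs between strata.

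**Conclusion.** The point holds as an inconsistency plus a cheap improvement in method. SAP 8.7.4 and Appendix 1 contradict the conditional rule in SAP 8.7.1 and protocol 10.4.3.2, and no treatment-by-subgroup comparison is specified for the GGT strata or for the interim GGT subgroups.

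The controlled overall conclusion is untouched. Across the readings considered, the chance of some nominally significant GGT result under no effect is about 9-18% at Week 24 and 21-37% at the interim. The upper ends assume every subgroup is analysed and read at two-sided 5% with equal SDs. The interim low end assumes Hochberg in each subgroup; at a plain 5% the lowest interim figure is 24%.

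The 45-64% discordance is the more useful number, because it does not rest on a multiplicity argument. It assumes normal data, 34 per arm, no missing data, a low-GGT share of 20-50% and stratum tests at 5%.

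**What to change.** - SAP 8.7.4 and Table 14.2-1.3.1.2: fit the primary ANCOVA with an added treatment-by-stratum term. Report the dose-placebo difference in each stratum and the interaction estimate, all with confidence intervals, as exploratory results that do not support an efficacy claim.
- If the van Elteren fallback is used: keep the stratum analysis that the protocol specifies, reported as stratum-specific location-shift estimates with confidence intervals.
- SAP 9: use the same layout and status for the interim GGT subgroups.
- Reconcile SAP 8.7.1 with 8.7.4 and Appendix 1 on whether the stratum analysis is conditional. If it is to be unconditional, list it in SAP 10 as a change from the protocol.

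The cost is SAP wording and one model term, with no new data and no change to the primary analysis. The downside is that the interaction estimate will be imprecise, so a wide interval must not be read as evidence that the effect is the same in both strata.

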8.8 PHARMACOKINETIC/ PHARMACODYNAMIC ENDPOINTS AND ANALYSES

Plasma concentrations of GKT137831 and its main phase 1 metabolite GKT138184 will be summarized using descriptive statistics by received dose level and planned visit. Any plasma concentrations below the limit of quantification will be considered as 0 for the calculation of the summary statistics.

The actual sampling time will be presented in listings. Pre-dose samples collected post dose will automatically be flagged for exclusion in the summary statistics.

Samples will be analyzed to determine plasma drug concentrations and thus to aid investigation of any PK/PD relationship with PD and/or efficacy endpoints, and optionally for the relationships between plasma drug concentrations and pharmacogenomics data.

A population PK model describing the plasma concentrations of GKT137831 and GKT138184 will be developed using non-linear mixed-effects modelling.

Relationships between drug concentrations/exposure measures and selected PD and/or therapeutic efficacy endpoints in the same subject will be graphically explored and formal PK/PD (exposure-response) analyses may be performed.

A separate Modeling and Simulation Analysis Plan (MSAP) for the PK/PD modeling describing the general approach to be taken will be finalized prior to database lock. The actual execution of any PK/PD modeling will depend upon the data, and full details of this will be provided in a separate report, which will be appended to the clinical study report (CSR).

